2.2 Therapeutic Intervention

A number of governing bodies now endorse an active rehabilitation program of progressive reintroduction of noncontact aerobic activity that does not exacerbate symptoms along with close monitoring of symptom expression.²²

In order to promote this, ANSwers Neuroscience Pty Ltd has developed a novel therapeutic intervention, downloadable to an Apple i-touch or i-phone device, that provides a telemetry-based graded exercise program which enables remote monitoring of symptoms. The sponsor will provide an i-touch or i-phone to each eligible subject during the Baseline Visit, which they will use daily during the 8 weeks of clinical study. Subjects keep the i-touch or i-phone on completion of study participation. The digital therapeutic application permits the ‘dosing of heart rate (HR)’ approach²³ while monitoring symptomatic and physiologic recovery on a daily basis. It is hypothesized that the mobile application, ClearPlay©, will accelerate recovery time following concussion by improving activity-induced blood flow to the brain and aid in the rehabilitation process. ClearPlay© is intended to be used in a professional setting following point of injury or onset of the condition and can also be used by patients at home. Refer to Figure 1 for an image of the ClearPlay© interface.

Figure 1: Sample of ClearPlay© Interface

To support the use of ClearPlay©, ANSwers Neuroscience Pty Ltd has developed 2 devices:

- ClearHeart©, a Cooling Glove System as an alternative to ice bucket testing, to enable providers to perform a quick, real-time diagnosis of autonomic nervous system disorders, including mTBI. The results are available immediately through a computer interface, permitting healthcare providers to make immediate diagnostic assessments and therapeutic recommendations.
- ClearNeck© a prototype device for cervico-genic proprioception measurement. This test is based on the joint position error test to assess “whiplash”.

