To validate the performance of ClearHeart© against ice bucket testing.	
 • Bland-Altman plots will be used to evaluate the agreement between HR measured by ClearHeart© and ice bucket testing. • Bland-Altman plots will be used to evaluate the agreement between BP measured by ClearHeart© and ice bucket testing.
To validate the performance of ClearNeck© against examination of the neck	
 • Correlations will be used to assess the association between results obtained through ClearNeck© testing and those obtained during the neurologic examination for neck range of motion and tenderness.

Abbreviations: ASI = Anxiety Sensitivity Index, BAI = Beck Anxiety Inventory, BCBT = Buffalo Concussion Bicycle Test, BESS = Balance Error Scoring System,; BP=blood pressure, BSI = Brief Symptom Inventory, CAARS = Conners' Adult Attention Deficit Hyperactivity Disorder Rating Scale, CES-D = Center for Epidemiologic Studies - Depression Scale,; HRV = heart rate variability; mTBI = mild traumatic brain injury; PCSS = Post-Concussive Symptom Scale, SNP = single nucleotide polymorphisms

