7.1.4 Vital Signs including Beat to Beat Blood Pressure

Vital signs will be collected via a third-party FDA approved device (Caretaker4®).³⁰ The subject will be fitted with the Caretaker4® device which attaches to right arm and right finger and measures continuous beat to beat HR and BP. Once connected, 2 minutes of baseline data collection will occur, followed by 2 minutes of ice bucket (or ClearHeart©) data collection, and a further 2 minutes post-ice bucket data collection.

The investigator (or a qualified observer at the investigational site) will interpret the vital signs using one of the following categories: within normal limits, abnormal but not clinically significant, or abnormal and clinically significant (reported with corresponding AE).

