7.5 Autonomic Tests

7.5.1 Cold Pressor Test (Ice Bucket and ClearHeart© Testing)

The cold pressor test measures the cardiovascular response to acute cooling of the hand. The cold pressor test will be performed using 2 different tests, with a break in-between each test (refer to Section 8.1 for details of the order of assessments to achieve this).

Ice Bucket Testing: The subject will rest in the supine position for at least 3 minutes. The subject will be fitted with the Caretaker4® device which attaches to right arm and right finger and measures continuous beat to beat HR and BP. Once connected, 5 minutes of baseline data collection will occur, followed by 2 minutes data collection while the subjects' left hand will be submerged in ice water for 120 seconds (ice bucket testing), and a further 2 minutes post-ice bucket data collection.

Testing with ClearHeart©: ClearHeart© is ANSwers Neuroscience Pty Ltd commercial prototype for cold pressure testing. The subject will rest in the supine position for at least 3 minutes. The subject will be fitted with the Caretaker4® device which attaches to right arm and right finger and measures continuous beat to beat HR and BP. Once connected, 5 minutes of baseline data collection will occur, followed by 2 minutes data collection while the subjects' left hand will be placed in the hand cooling device (ClearHeart©) for 120 seconds, and a further 2 minutes ClearHeart© data collection.

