9.3.3 Efficacy Population

The efficacy population will include all randomized subjects who completed, at least Day 1 of therapeutic intervention, who had PCSS data at baseline and at least 1 post-baseline assessment and will be based on the actual therapy received. The efficacy population will be

used for the summaries of all neuropsychology and autonomic data, and for the validation of ClearHeart© and ClearNeck© performance.

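### The ClearHeart agreement endpoint is not tied to the response to cooling; its resting window is stated two ways, and its analysis set discards valid pre-randomisation pairs

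*Protocol*

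**What the plan says.** Section 3.2 lists validation of ClearHeart against ice bucket testing as a secondary objective. Table 1 in section 4.2, repeated in the synopsis, gives two endpoints: "Bland-Altman plots will be used to evaluate the agreement between HR measured by ClearHeart© and ice bucket testing" and "Bland-Altman plots will be used to evaluate the agreement between BP measured by ClearHeart© and ice bucket testing". Neither names a recording window, or says whether a level or a change is compared.

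Other sections describe the device and the test:

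- Section 2.2 calls ClearHeart "a Cooling Glove System as an alternative to ice bucket testing".
- Section 7.5.1 has the subject, in each of the two tests, "fitted with the Caretaker4® device which attaches to right arm and right finger and measures continuous beat to beat HR and BP".
- Section 7.5.1 states the purpose: "The cold pressor test measures the cardiovascular response to acute cooling of the hand".
- On the rest period, section 7.5.1 says for each test that "5 minutes of baseline data collection will occur", while section 7.1.4 says that "2 minutes of baseline data collection will occur" for the ice bucket or ClearHeart.
- Table 4 in section 8.1 puts neuropsychology testing, the neurologic evaluation and ClearNeck between the two cold tests. It swaps their order by odd or even subject number and places both before randomisation.
- Section 9.3.3 defines the efficacy population by completion of Day 1 therapy, baseline PCSS data and at least one post-baseline assessment. This set is to be "used for the summaries of all neuropsychology and autonomic data, and for the validation of ClearHeart© and ClearNeck© performance".

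**The concern.** The endpoint attributes the heart rate and BP readings to ClearHeart, but ClearHeart is the stimulus and the Caretaker4 is the sensor in both arms of the comparison. Read literally, one sensor is compared with itself on two occasions. The question that matters for the device, whether glove cooling provokes the same cardiovascular response as ice water, is not in the endpoint.

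The protocol does separate level from response elsewhere: section 9.6 uses the BP change during the ice bucket test, but only to check the randomisation. The changes from baseline in section 9.6.2 do not fill the gap. They belong to summaries by treatment group, and section 9.2 defines baseline as the last assessment before the intervention, not the rest period within a test.

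At stake is whether the limits of agreement describe the device or a mixture of the device and how far the subject's resting state moved between sessions. Any change score also needs a settled resting window, and the protocol gives two.

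**Working it through.** The protocol gives no agreement limit, SD or sample size for this objective, so there is no figure to reproduce. All SDs below are assumptions.

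**What the difference contains.** For one subject, the cooling-window level is the resting level plus the response. Between the two tests:

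level difference = difference in resting level + difference in response

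Subtracting each test's own resting window leaves only the difference in response, plus measurement noise.

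**Limits of agreement.** Let d be the SD of the between-test difference in resting level, r the SD of the between-test difference in response, and e the noise SD of a window mean. Take d and r as independent, and e as equal in all windows. A level difference uses two window means and a change difference uses four:

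- Levels: ±1.96 × √(d² + r² + 2e²)
- Change: ±1.96 × √(r² + 4e²)

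With r = 5 mmHg:

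| d (mmHg) | Levels, e = 1 | Change, e = 1 | Levels, e = 3 | Change, e = 3 |
|---|---|---|---|---|
| 0 | ±10.2 | ±10.6 | ±12.9 | ±15.3 |
| 3 | ±11.8 | ±10.6 | ±14.1 | ±15.3 |
| 5 | ±14.1 | ±10.6 | ±16.2 | ±15.3 |
| 8 | ±18.7 | ±10.6 | ±20.3 | ±15.3 |
| 12 | ±25.6 | ±10.6 | ±26.8 | ±15.3 |

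Example: d = 8, e = 1 gives 1.96 × √(64 + 25 + 2) = 18.7 on levels and 1.96 × √(25 + 4) = 10.6 on change.

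**Where the advantage turns.** Change is narrower when d² + 2e² > 4e², that is, when d > √2 × e: about 1.4 mmHg for e = 1 and 4.2 mmHg for e = 3. At d = 4 and e = 3 the two are level: 1.96 × √(16 + 25 + 18) = 15.1 against 1.96 × √(25 + 36) = 15.3.

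**Order of tests.** Odd/even alternation puts a systematic first-to-second shift into the differences with opposite signs, so it roughly cancels in the mean difference. It still widens the limits of a level plot. An assumed shift of ±5 mmHg with r = 5 and no noise gives 1.96 × √(25 + 25) = ±13.9 instead of 1.96 × 5 = ±9.8.

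**Why the window matters.** If the whole recording were averaged, cooling would fill 2 of 9 minutes (5 + 2 + 2; 22%) under section 7.5.1, or 2 of 6 minutes (2 + 2 + 2; 33%) under section 7.1.4. An assumed 10 mmHg weaker response to ClearHeart, with no effect after cooling, would then appear as 10 × 2/9 = 2.2 mmHg or 10 × 2/6 = 3.3 mmHg. The protocol does not say that the record is averaged this way; the point is only that the result depends on a window the endpoint leaves open.

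**Analysis set.** Both Day 0 tests are finished before allocation (sections 4.1, 6.3.2 and 8.1), so completing Day 1 therapy or giving later data has no bearing on whether a Day 0 pair is valid. As an illustration, if the whole 15% attrition allowance of section 9.1 were lost from 400 subjects, 340 pairs would remain and the standard error of the limits would rise by a factor of √(400/340) = 1.08, about 8%.

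**The case against.** The strongest reply is that the protocol never says levels are plotted. A response-based plot is consistent with the purpose stated in section 7.5.1, and the exact quantity in a Bland-Altman plot is commonly fixed in the SAP, which is not at hand. Attributing the readings to ClearHeart may be shorthand for readings taken during the ClearHeart test. This stands in part. A reader might infer that the protocol commits to comparing levels; it does not. What remains is that the endpoint as worded misdescribes what ClearHeart does and omits the response.

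Three other stronger readings also fail:

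- A reader might infer that the plan cannot tell a weaker stimulus from resting drift. The alternating order largely protects the mean difference, so a weaker stimulus would still show as bias in a comparison of cooling-window levels. Each test is also preceded by at least 3 minutes of supine rest. The limits are what remain exposed.
- A reader might infer that the device could wrongly pass or fail. The protocol sets no agreement limit, so there is no rule to pass or fail.
- A reader might infer that change scores always give tighter limits, or that the two tests use different resting windows. The table shows the first is conditional. On the second, each section gives the same window to both tests; the conflict is between sections.

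The exclusion in section 9.3.3 is narrow, since later dropouts stay in.

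**Conclusion.** The point holds in limited form. The endpoint names heart rate and BP as if ClearHeart measured them and does not tie agreement to the cooling response. If levels were used, resting differences between sessions would enter the limits; that follows from the algebra. How much they would widen the limits is unknown: with r = 5, the ratio of level limits to change limits runs from 0.84 to 2.43 over the assumed drift SDs of 0 to 12 mmHg and noise SDs of 1 and 3 mmHg. The case for change rests on its isolating the effect of the stimulus, not on narrower limits.

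The 2-minute against 5-minute conflict is on the face of the protocol. The restriction to the efficacy population has no rationale for Day 0 pairs, but its cost in precision is probably small. One secondary device objective is affected; the comparison of exercise with stretching is not.

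**What to change.** 1. In Table 1 and the synopsis, state the compared quantity as the cooling-window value minus the resting-window value from the same test, for heart rate and for BP, recorded by the Caretaker4 under each cooling method. Keep window levels as a supportive display.
2. Reconcile sections 7.1.4 and 7.5.1 on the length of the resting window.
3. Run the Day 0 agreement analysis on all subjects with both Day 0 tests, regardless of later therapy or PCSS entries. Table 5 schedules both tests again at Day 56; report those pairs separately.

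The cost is a wording change, one reconciled window and a separate analysis set; the recordings are already planned. The downside is that change scores carry added noise from the resting measurement, so their limits may be as wide as those on levels, or wider, when drift is small relative to noise.

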3.3 Exploratory Objectives

The exploratory objectives of the study are to:

- Validate the performance of ClearNeck©, ANSwers Neuroscience Pty Ltd commercial prototype based on the joint position error test to assess “whiplash”.

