In addition, a set of single nucleotide polymorphisms (SNP) and micro ribonucleic acids (RNA) that have been implicated in contributing to the biologic vulnerability to PPCS will be analyzed. Deoxyribonucleic acid (DNA) and RNA will be isolated for bio-banking and subsequent analysis. Sample collection will be either blood collection or buccal swab and collection of saliva.

New tests, ClearHeart© and ClearNeck© will be validated as part of the study objectives by comparing against the equivalent validated methods, Ice Bucket Testing and neurological examination respectively, which will be also be performed as part of the study.

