7.6.1 Whiplash Test (Whiplash Testing (ClearNeck©))

The ClearNeck© is ANSwers Neuroscience Pty Ltd commercial prototype for cervico-genic proprioception measurement. The subject will be seated 40 to 50 cm from a bullseye target, and the ClearNeck© (cap with inbuilt laser) will be placed on the subject's head. During testing, the subject will direct the laser onto the target from zero angle (by looking straight ahead with eyes open), and 8 trials (4 left and 4 right) of proprioception (eyes closed, rotate head 90 degrees to the left or right, then back to starting point).

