7.6.2 Neurologic Examination

The neurologic examination, by an allied health professional, will include performing the following neurological tests:

- Orthostatic Vital signs: Blood pressure, Heart Rate and Symptoms are measured Supine after 2 minutes rest and Standing after 1 minute rest. Test results are deemed clinically significant if they include at least one of the following AND symptomatic: (1) systolic BP drop of ≥ 20 mmHg or (2) diastolic BP drop of ≥ 10 mmHg.
- Neck and Sub-Occipital Region Exam: Evaluation of neck muscle spasm, tenderness, and range of motion, to evaluate for any signs or symptoms of whiplash
- Oculomotor/Ophthalmologic Evaluation: Evaluations of visual tracking, smooth pursuits, repetitive saccades, gaze stability, and near point of convergence (NPC) and accommodation.
- Postural Control and Motor Coordination: Evaluation of tandem gait with eyes open and closed, and tandem stance.

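### ClearNeck's correlation with neck range of motion and tenderness offers weak convergent evidence; it does not validate the device's joint-position measurement

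*Protocol*

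**What the plan says.** Section 2.2 introduces ClearNeck as "a prototype device for cervico-genic proprioception measurement". Section 3.3, where it is the only exploratory objective, calls it a "commercial prototype based on the joint position error test to assess" whiplash. In 7.6.1 the subject wears a cap with a laser, closes the eyes, turns the head 90 degrees and returns to the start, four times to each side. The set-up is given as "The subject will be seated 40 to 50 cm from a bullseye target".

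Table 1 in 4.2, and the synopsis, list validation of ClearNeck among the secondary objectives. The endpoint is the correlation of its results with "those obtained during the neurologic examination for neck range of motion and tenderness". Section 4.3 says the two new devices will be validated by "comparing against the equivalent validated methods, Ice Bucket Testing and neurological examination respectively". The neck part of that examination, in 7.6.2, consists of "Evaluation of neck muscle spasm, tenderness, and range of motion".

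**The concern.** The device and its reference measure different things. One concerns the sense of head position; the other concerns pain, spasm and how far the neck moves. If the second is accepted as an equivalent method for the first, a sizeable correlation could be reported as proof that the sponsor's prototype measures accurately, and a small one as evidence that it does not. Neither conclusion would follow.

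A statistical analysis plan could add a target correlation, but it cannot supply the missing reference measurement, because the assessments are fixed in the protocol.

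**Working it through.** The plan states no figure on this point, so there is none to reproduce. The check sets the protocol's descriptions side by side and then asks what a correlation between them could show.

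**Step 1. The two measurements.**

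| | ClearNeck (2.2, 3.3, 7.6.1) | Neck examination (7.6.2) |
|---|---|---|
| Quantity | "commercial prototype for cervico-genic proprioception measurement" | "Evaluation of neck muscle spasm, tenderness, and range of motion" |
| Task | Eyes-closed turn and return to start, 8 trials | Evaluation of the neck and sub-occipital region |
| Clinical target | Whiplash | Whiplash |
| Timing (Table 5) | Day 0 and Day 56 | Day 0 and Day 56 |

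The clinical target is shared; the quantity is not. Section 7.6 groups both tests under neck range and motion, but the turn in 7.6.1 is set at 90 degrees and the task is the return, so range is not what it tests. The rest of the neurologic examination (orthostatic signs, eye movements, tandem gait and stance) has no neck joint-position item either. Tables 4 and 5 list no other neck test.

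**Step 2. The contrast with ClearHeart.** Table 1 compares heart rate with heart rate and blood pressure with blood pressure, using Bland-Altman plots. Agreement can be assessed because both methods yield the same quantity. For ClearNeck no agreement analysis is possible, and only association remains.

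**Step 3. What the correlation can show.** A constant offset or a wrong scale in the device leaves a correlation unchanged. Random error shrinks it:

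observed r = ρ × √(device reliability × examination reliability),

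where ρ is the true correlation between joint-position error and the clinical neck signs. The protocol gives none of these inputs. Assumed here: ρ from 0 to 0.7; examination reliability 0.5 to 0.8; device reliability 0.9 (accurate) or 0.4 (poor).

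| ρ | r, accurate device | r, poor device |
|---|---|---|
| 0 | 0.00 | 0.00 |
| 0.3 | 0.20 to 0.25 | 0.13 to 0.17 |
| 0.5 | 0.34 to 0.42 | 0.22 to 0.28 |
| 0.7 | 0.47 to 0.59 | 0.31 to 0.40 |

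Take examination reliability 0.5. An accurate device with ρ = 0.3 gives 0.3 × √(0.9 × 0.5) = 0.20. A poor device gives 0.4 × √(0.4 × 0.5) = 0.18 at ρ = 0.4 and 0.5 × √(0.4 × 0.5) = 0.22 at ρ = 0.5. An observed r of about 0.2 therefore does not tell the two apart. With ρ = 0, even a perfect device gives r = 0.

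**Step 4. Would significance help?** With all 400 subjects the smallest r reaching two-sided p < 0.05 is tanh(1.96/√397) = 0.098. With the protocol's 15% attrition (400 × 0.85 = 340) it is tanh(1.96/√337) = 0.106. A very weak association would be significant, so a p-value does not settle the matter.

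**Step 5. Seating distance.** An angular error θ displaces the laser spot by distance × tan θ. For any θ, the ratio between the extremes of the permitted range is 50/40 = 1.25. The same error is thus up to 25% larger on the target at 50 cm than at 40 cm. This matters only if the result is read as a distance; 7.6.1 gives neither the unit nor an instruction to record the seating distance.

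**The case against.** The best defence is that both tests are aimed at whiplash, and that relating a new test to established clinical signs of the same condition is ordinary convergent evidence. The endpoint's own wording is modest: it speaks of association, and keeps agreement methods for ClearHeart, where the quantities match. This stands. A reader might infer that the comparison is worthless or that the endpoint cannot be answered. The documents do not support that: the association can be estimated and carries some information about whether ClearNeck tracks clinical neck signs.

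A reader might also infer that a low correlation would fail a good device. Table 1 sets no threshold and no pass/fail rule, so the protocol does not commit anyone to that step.

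Third, 3.3 lists the objective as exploratory, and nothing in the primary comparison depends on it. This too stands, and it lowers the priority. But Table 1 and the synopsis place the same objective among the secondary ones, so the protocol is not consistent about its status.

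Finally, seating distance is a separate and conditional matter. Conversion to degrees may already be intended, and the point adds nothing to the argument about what is measured.

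The defence does not rescue the equivalence claim in 4.3 or the word *validate*. An examination with no joint-position item is not an equivalent method for a joint-position test.

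**Conclusion.** The concern holds as a limit on what may be claimed. The planned correlation can give weak convergent evidence that ClearNeck relates to clinical signs of whiplash. It cannot establish or refute the accuracy of its joint-position measurement, and the protocol schedules no reference that could. This conclusion rests on the protocol's own descriptions of the two tests. The correlations in the working rest on assumed reliabilities and only illustrate it.

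The seating effect is at most 25%, at the extremes of the permitted range, and only if error is scored as a distance on the target. Priority is low.

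**What to change.** - In Table 1, the synopsis and 4.3, replace the validation and equivalence wording for ClearNeck with exploratory association with clinical neck signs. Sections 3.3 and 9.3.3 also speak of validation and should follow.
- Reconcile the status of the objective: exploratory in 3.3, secondary in Table 1 and the synopsis.
- Add within-session repeatability of position error from the 8 trials already recorded (within-subject SD or intraclass correlation, by side). State that this shows repeatability and not accuracy.
- In 7.6.1, record the seating distance and express error in degrees, as arctan(displacement/distance).

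The cost is wording in the protocol and analysis plan, one extra recorded value per test and a short additional analysis. No new test, visit or subject is needed. The downside is a more modest claim for the device. A claim of accuracy would need an independent joint-position reference, which this trial does not collect.
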